origin in the Declaration of Helsinki. This clinical investigation will be conducted in compliance with Good Clinical Practice (GCP), ISO 14155 and MDR (EU) 2017/745.

D. Investigator Approval and Agreement

PROTOCOL SIGNATURE PAGE

The signature below constitutes the receipt, review and understanding of the protocol entitled, "The RAVI Registry: A Prospective, Multi-Center, Observational Study of Radial Access Embolization Procedures Using HydroPearl Microspheres" and any attachments, and provides the necessary assurances that this study will be conducted according to all stipulations of the signed Clinical Trial Research Agreement (CTRA), protocol, including all statements regarding confidentiality, and according to local legal and regulatory requirements and applicable U.S. federal and European regulations (MDR (EU) 2017/745).

Investigator Signature

Date

Investigator Name (please print)

Investigator Institution (please print)

E. Study Synopsis

Study Title	The RAVI Registry: A Prospective, Multi-center, Observational Study of Radial Access Embolization Procedures Using HydroPearl Microspheres.
Study Number	TIS2019-02
Study Sponsor	Terumo Medical Corporation [name] USA
Study Objective	The objective of this registry study is to assess the procedural success and complication rates in real-world patients undergoing HydroPearl embolization procedures via radial access.
Study Design	Multicenter, prospective, non-randomized post-market registry
Procedure(s):	Embolization of hypervascular tumors and arteriovenous malformations, including uterine fibroids and prostate artery embolization for symptomatic benign prostatic hyperplasia, via radial access.
Subject Population	Up to 100 subjects with procedures planned using radial artery access
Study Duration	Study enrollment is expected to take up to 18 months. Primary endpoint data will be collected at 30 days post-procedure, 180 days post-procedure, and 365 days post-procedure.
Primary Study Evaluations	
1. Procedural success defined as completing the planned procedure without femoral access bailout2. Technical success defined as delivery of HydroPearl to the target vessel and slowing the blood flow with microsphere embolization.3. Freedom from Major Adverse Events within 30 days of procedure, defined as:
a. Deathb. MIc. Stroke4. Freedom from radial access related complications at 30 days, defined as:
a. Radial artery occlusion (reverse Barbeau and/or Ultrasound, per site standard of care)b. Hand ischemiac. Arteriovenous fistulad. Pseudoaneurysme. Any complication requiring surgical and/or endovascular intervention within 30 days of index procedure
Additional Evaluations	
1. Incidence of Radial Artery Occlusion Complications at any time
a. Arteritis

	
b. Cellulitisc. Ecchymosisd. Pain at puncture sitee. Hematoma 
2. Quality of Life and Health Economics3. Procedural endpoints:
a. Blood lossb. Patient radiation exposurec. Contrast volumed. Time to hemostasise. Total procedural timef. Time to dischargeg. Operative timeh. Radial cocktail components and frequency of administration4. Access endpoints:
a. Radial artery spasmb. Time to dischargec. Radial access pain VAS5. Closure endpoints
a. Time to hemostasisb. Time to ambulation
Procedure Evaluations	
1. Tumor type2. Number and size of tumors / fibroids3. Post embolization syndrome4. UFE:
a. If post-op MRI is obtained per standard of care: Effectiveness of HydroPearl measured by MRI.
i. Infarction is characterized by complete (100%), 90-99%, 50-89%, or less than 50%.ii. Uterine Volumeiii. Dominant Fibroid Volumeb. EQ-5Dc. UFS-QoLd. Return to normal activitiese. Pain VASf. Symptoms including bleeding and bulkg. Pregnancy intention and occurrence5. Prostate Artery Embolization:
a. IPSS with Quality of Lifeb. EQ-5Dc. Return to normal activitiesd. Pain VAS

	
e. Qmaxf. Prostate volume6. Liver Tumor Embolization:
a. Tumor response (CR, PR, SD, PD)b. EQ-5Dc. Return to normal activitiesd. Pain VASe. Disease stage7. Other Hypervascular tumors
a. Infarctionb. Return to normal activitiesc. Pain VAS8. Arteriovenous malformations:
a. EQ-5Db. Return to normal activitiesc. Pain VAS
Inclusion Criteria	
1. Subject is \geq 18 years old2. Subject is scheduled for an embolization procedure for treatment with HydroPearl microspheres via radial access.3. Subject is willing and able to complete follow-up requirements4. Subject is willing and able to sign a written Informed Consent form prior participating in the registry.
Exclusion Criteria	
1. Unable to have a procedure with radial access for any reason.2. Participating in another clinical study which, in the opinion of the investigator, could impact the results of this registry.3. Pregnant or planning to become pregnant during the study.
Statistical Analysis	
Endpoints will be reported with descriptive statistics as well Kaplan-Meier survival curves where appropriate.
 
Sub-group analyses include, but are not limited to:
 
• UFE procedure• PAE procedure• Liver embolization procedure• Other hypervascular tumors procedure• AVM embolization procedures
Imaging Assessments	Imaging datasets will be conducted for baseline, procedure, and follow-ups per site standard of care and results entered into eCRF. Images will not be collected or archived by the Sponsor.
Safety	The Principal Investigator at each site will be responsible for reviewing and following any adverse events per site standard of care.
Data Quality	Electronic case report forms will be used to collect data evaluations in this registry.

	Source data verification will be completed during periodic on-site monitoring visits. The frequency of on-site visits will be specified in the study monitoring plan.					
Schedule of Events						
Assessment	Screening / Baseline	Procedure	Discharge	30 Day Follow-up ±14 days	180 Day and 365 Day Follow-ups ±30 days	
Informed Consent	X					
Eligibility Criteria	X					
Medical History/Demographics	X					
Pregnancy Test	X					
Blood Tests (if available)	X	X	X	X	X	
Imaging (if available)	X	X	X	X	X	
Physical Exam	X		X	X	X	
Procedural, access, closure evaluations		X				
QoL questionnaires and return to normal activities	X		X	X	X	
Concomitant Medications (Anticoagulation / Antiplatelets Only)	X	X	X	X		
Device Related Adverse Events		X	X	X	X	

F. List of Abbreviations and Definition of Terms

AE:	Adverse Event
AV:	Arteriovenous
BMI:	Body Mass Index
BPH:	Benign Prostatic Hyperplasia
CEC:	Clinical Events Committee
CFR:	Code of Federal Regulations
CIP:	Clinical Investigational Plan, also referred to as (study) protocol
CRO:	Clinical Research Organization
CTRA:	Clinical Trial Research Agreement
eCRF:	Electronic Case Report Form
EQ-5D:	EuroQol Group standardized measure with 5 dimensions
HIPAA:	Health Care Portability and Accountability Act
ICF:	Informed Consent Form
ICH:	International Conference on Harmonization
IFU:	Instructions for Use
IRB/EC:	Institutional Review Board/Ethics Committee
IPSS:	International Prostate Symptom Score
MI:	Myocardial Infarction
mRECIST:	Modified Response Evaluation Criteria in Solid Tumors
PAE:	Prostate Artery Embolization
PG:	Performance Goal
QoL:	Quality of Life
SAE:	Serious Adverse Event
SDV :	Source Document Verification
UADE:	Unanticipated Adverse Device Effect
UFE	Uterine Fibroid Embolization
UFS-QOL:	Uterine Fibroid Symptom Quality of Life Questionnaire
VAS	Visual Analog Scale

1 Background

The transradial approach to percutaneous interventions has generated intense interest over the past decades. Initially researched in the context of percutaneous coronary interventions (PCI), early reports of successful transradial access (TRA) included coronary angiography in 1989 (Campeau, 1989) and the first successful TRA coronary angioplasty and stent implantation in the years 1992 and 1993, respectively. (Kiemeneij & Laarman, 1993).

Further studies of TRA for PCI have consistently demonstrated its benefits as compared to femoral access, including decreased bleeding, access site complications and post-procedure recovery time, and increased patient satisfaction and cost effectiveness. (Rao, Cohen, Kandzari, Bertrand, & Gilchrist, 2010) . Limitations to the transradial approach have been recognized, such as a learning curve which must be overcome by new operators, limitations of available equipment suitable for radial use, and relatively rare complications such as localized access site hematoma. Radial artery occlusion is reportedly rare and upon occurrence is often asymptomatic due to collateral perfusion supplied by the ulnar artery. (Fischman, Swinburne, & Patel, 2015).

The benefits of transradial access are considered by many physicians to outweigh these drawbacks, leading to the steady uptake of TRA for PCI; an estimated 16% of PCI procedures in the US were conducted transradially in the year 2012, up from 1.2% in 2007. Within the previous decade, additional support for TR-PCI has been generated by multiple prospective, randomized trials, including the RIFLE, RIVAL and MATRIX trials which have consistently demonstrated decreased access site bleeding and net adverse events.

(Fischman, Swinburne, & Patel, 2015). The expanding body of evidence favoring transradial access for PCI prompted physicians to branch beyond the coronary space to transradial access for visceral and peripheral arterial interventions, (Rao, Cohen, Kandzari, Bertrand, & Gilchrist, 2010) and more recently, for interventional radiology procedures, such as embolization of hypervascular tumors, including uterine fibroids and liver tumors ((Yamada, et al., 2018)).

Uterine fibroid embolization, traditionally achieved via femoral access, is considered by the American College of Obstetrics and Gynecology as a safe, minimally invasive primary treatment for symptomatic uterine fibroids. (Keung, Spies, & Caridi, 2018) . The first reported series of UFE achieved via radial access dates to 2014, where Resnick, et al. (2014) conducted UFE on 29 patients at a single institution with a 100% success rate. No immediate major or minor complications were observed in any patients, and radial artery patency was evident in all patients at one month follow up. (Resnick, et al., 2014). Recently,

Gjoreski, et al. (2019) directly compared the safety and feasibility of UFE when achieved through radial as opposed to femoral access. In this retrospective study, 13 femoral procedures and 11 transradial procedures all yielded a 100% success rate with no significant difference in access site related and overall adverse events noted between cohorts. Procedure and fluoroscopy times were reportedly shorter in the radial group; a mean procedure time of 60.3 minutes was associated with the radial group as compared to 72.4 minutes in the femoral cohort, and mean fluoroscopy time was 21.1 minutes and 25.3 minutes in the radial and femoral cohorts, respectively. (Gjoreski, Gjoreski, & Nancheva, 2019).

The development of transradial access for embolization of hepatic tumors can be traced back to a 2003 report by Shiozawa et al. (2003) which described transcatheter arterial chemoembolization (TACE) in 327 patients, 177 of which were accessed radially and 150 via femoral access. Therapeutic efficiency was observed in both cohorts, with a lower complication rate in the radial cohort (4.6%) compared to the femoral (12.7%). (Shiozawa, et al., 2003). In addition to chemoembolization, radial access has also been utilized for radioembolization of hepatic tumors. A study by Fischman, et al. published in 2016 described 30 procedures conducted in 26 patients which supported the safety and tolerability of TRA for hepatic artery embolization. In this study, 14 TACE procedures, 14 Y90 procedures and 2 bland embolization procedures yielded a 100% technical success rate with no major AEs reported at one month follow up. (Fischman, et al., 2013) . In a 318 patient study, a total of 329 planning angiograms and 245 Y90 embolization procedures resulted in technical success in 97.7% of cases, superficial bruising observed in 2.3% of cases, and a radial artery occlusion rate of 1.6%. (Bishay, et al., 2016) .

A study by Kis and colleagues, comparing the feasibility of transradial vs transfemoral access for hepatic radioembolization, demonstrated 100% technical success in both radial and femoral cohorts, totaling 64 procedures in 50 patients. Direct savings in cost and time were noted in the radial group; approximately \$100 and 1-hour decrease post procedure stay was observed on a per procedure basis. Despite a caveat noted in this study surrounded the technical challenges associated with radial access which led to longer fluoroscopy time and greater radiation doses, the authors recommended radial access as the primary choice in selected patients, such as those with low platelet count and/or morbid obesity. (Kis, Mills, & Hoffe, 2016) The association between increased radiation exposure and fluoroscopy time with radial access was challenged in a later study, in which 124 intraarterial procedures were performed on 55 liver cancer patients, which demonstrated

significantly less radiation exposure to operators using radial artery access, and similar contrast agent volume and patient radiation exposure between groups. This randomized, prospective study was primarily conducted in order to assess patient access preference for intraarterial liver cancer therapies; of 36 patients who experienced at least one radial and one femoral access procedure, 81% preferred TRA compared to 19% who preferred TFA. (Yamada, et al., 2018)

A recent paper from an Italian University hospital from a study of 60 pts treated with TACE for HCC reported 0% of cross-over rate from trans-femoral access (TFA) to trans-radial access (TRA). A positive association between operator experience and time spent for fluoroscopy, puncture, procedure and total examination was noted. A negative relationship between TRA and contrast volumes and radiation exposure were also reported. A higher percentage of pts treated with TFA reported post-procedural complains at the puncture site and limitations in performing basic activities. The operator learning curve was estimated to be low, with an estimated threshold of 20 procedures. (Iezzi, et al., 2019)

The largest study involving safety and feasibility of transradial access for non-coronary interventions includes both UFE and hepatic artery embolization among other visceral interventions. In this single center study, 936 patients undergoing 1,512 consecutive TRA procedures were retrospectively analyzed. Of these procedures, UFE accounted for 116, and TACE, Y90 mapping and Y90 infusion accounted for 485, 391 and 293 procedures, respectively. Combined analysis indicated a technical success rate of 98.2%. Major complications, including one pseudoaneurysm and one seizure, were reported at 0.13%, and minor complications, including hematomas, RAO, RAS and arm pain, were observed in 2.38% of cases. Twenty-seven cases, representing 1.8%, required crossover to transfemoral access. The favorability of these results towards radial access led authors to pronounce TRA as a promising alternate primary access site in a variety of peripheral vascular interventions. (Posham, et al., 2016)

1.1 HydroPearl microspheres and Indications For Use

HydroPearl microspheres are indicated for use in arteriovenous malformations and hypervascula tumors, including uterine fibroids, and for prostate artery embolization for symptomatic benign prostatic hyperplasia (BPH).

1.2 Summary of Clinical Studies

No clinical studies using HydroPearl have been published, although a small retrospective study of 17 PAE patients treated with HydroPearl for BPH was presented at the Spectrum, an annual conference for IR (interventional radiology) oncological diseases.

2 Study Design, Sample Size and Duration

2.1 Study Design

This is a prospective, multi-center, non-randomized registry to record the real-world safety and efficacy of the HydroPearl microspheres for arteriovenous malformations and hypervasculat tumors including uterine fibroids, and for embolization prostatic arteries for symptomatic benign prostatic hyperplasia (BPH).

2.2 Sample Size

Up to 10 sites in the US and EU are expected to participate in the study with 100 subjects enrolled. Each study site will be limited to 30% of total patient population.

The target population is comprised of subjects scheduled for embolization procedures with HydroPearl microspheres used on-label via radial access.

2.3 Study Duration

Study enrollment is expected to occur over an 18-month period. Follow-up will continue for each subject through 365-days post-procedure.

3 Study Objective and Evaluations

3.1 Study Objective

The objective of this registry study is to assess the technical and procedural success and complication rates in real-world patients undergoing embolization procedures with HydroPearl microspheres via radial access.

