9.1 Risk Management Procedure

Subjects will be monitored for the duration of the study. Risks will be mitigated through selection of qualified physicians, appropriate training, and study monitoring ensured by the following:

- Investigators who participate in the study will be experienced and skilled in radial access for visceral interventions. Additionally, investigators, in conjunction with the investigational site, will have adequate resources for participation in a registry study.
- Each investigator will ensure oversight and approval of the study by their IRB/EC prior to initiation of the study at their site.
- The investigator and study personnel will be trained on the study protocol.
- Subjects will be carefully evaluated against the eligibility criteria prior to entering the study to ensure that their diagnosis and medical status are appropriate for participation.

- Subjects will be monitored throughout the follow-up period as defined in the study protocol. Subjects will have visits with the investigator or designee to review the subjects' status.

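### The registry aims at real-world rates but neither requires consecutive enrollment nor logs eligible patients who are not enrolled, so selection within a site could not be seen

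*Combined protocol and SAP*

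**What the plan says.** - **Aim.** Section 3.1 seeks technical and procedural success and "complication rates in real-world patients undergoing embolization procedures with HydroPearl microspheres via radial access". Section 2.1 also describes the registry as recording real-world safety and efficacy.
- **Target population.** Section 2.2: "The target population is comprised of subjects scheduled for embolization procedures with HydroPearl microspheres used on-label via radial access".
- **Size and spread.** Section 2.2: "Up to 10 sites in the US and EU are expected to participate in the study with 100 subjects enrolled", and "Each study site will be limited to 30% of total patient population". Section 2.3 expects 18 months of enrollment.
- **How subjects are found.** Section 4.2 (Subject Enrollment) gives only the number of sites and subjects. Sections 4.1.1 and 4.1.2 list four inclusion and three exclusion criteria. The first exclusion covers anyone who cannot have radial access, whatever the cause.
- **Who is counted.** Section 4 starts enrollment when the guidewire enters the radial artery. Section 13.3 describes enrolled subjects by consent and eligibility and then keeps those treated. Section 13.6 mentions screening failures only among people who signed consent, and leaves them out of the analyses.
- **Operators.** Section 9.1: "Investigators who participate in the study will be experienced and skilled in radial access for visceral interventions". Section 1 notes "a learning curve which must be overcome by new operators" and, from one liver-tumor series, reports: "The operator learning curve was estimated to be low, with an estimated threshold of 20 procedures".

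**The concern.** The study tests no hypothesis (Sections 13.1 and 13.7). What it delivers is a set of descriptive rates, and their value depends on whether the 100 subjects represent the patients named in Section 2.2. Nothing in the protocol ties enrollment to a site's caseload. A site that left out patients it expected to be difficult would break no rule, so the deviation summaries in Section 13.8 would not show it. The monitors' tasks listed in Section 10 include no comparison of enrollment with caseload.

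Failures are expected to be few, so a small number of omitted patients could move the reported rates. Without a record of who was eligible, a reader of the final report could not tell whether that had happened, and such a record cannot be reliably rebuilt after enrollment closes.

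**Working it through.** **1. The plan's own figure.** Section 13.1 claims more than 80% probability of seeing at least one major complication in 100 evaluable patients at a population rate of 1.6%. Exact binomial: 1 − (1 − 0.016)^100 = 1 − 0.984^100 = 0.8007. The figure reproduces. It presumes that the enrolled patients carry the population rate.

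**2. What that presumption carries.** Assume that selection multiplies the enrollees' rate by r. The probability becomes 1 − (1 − 0.016r)^100:
- r = 1: 80.1%
- r = 0.9: 76.6%
- r = 0.75: 70.1%
- r = 0.5: 55.2%

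The documents give no value for r.

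**3. Room for selection.** 100 subjects / (10 sites × 18 months) = 0.56 enrollments per site per month on average. Site caseload is not stated. A site treating more eligible patients than it enrolls has room to choose.

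**4. Possible size.** Assume an enrolled rate of 1.6%, a share f of eligible patients passed over, and k times the enrollees' risk in those patients. The rate in all eligible patients is (1 − f) × 1.6% + f × k × 1.6%:

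| f | k | Rate in all eligible |
|---|---|---|
| any | 1 | 1.6% |
| 10% | 2 | 0.9 × 1.6 + 0.1 × 3.2 = 1.76% |
| 30% | 2 | 0.7 × 1.6 + 0.3 × 3.2 = 2.08% |
| 50% | 3 | 0.5 × 1.6 + 0.5 × 4.8 = 3.2% |
| 30% | 0.5 | 0.7 × 1.6 + 0.3 × 0.8 = 1.36% |

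Both f and k are assumptions. The last row shows that the direction is open as well.

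**5. Scale.** Exact (Clopper-Pearson) 95% intervals at n = 100 are 0 to 3.6% for 0 events and 0.24% to 7.0% for 2 events. Every rate in the table lies inside both. The largest shift, 3.2 − 1.6 = 1.6 points, compares with 7.0 − 2.0 = 5.0 points above and 2.0 − 0.24 = 1.76 points below an observed 2%.

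**6. Would the existing provisions show selection?**
- The 30% cap (Section 2.2) limits one site's share of the total. It does not govern choice within a site.
- The by-site tables and site-effect model (Section 13.4) use enrolled patients only.
- The 95% intervals (Section 13.2) express sampling error only.
- Consented screening failures (Section 13.6) are recognized, but no reporting of their number or reasons is specified, and patients never asked for consent do not appear at all.

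**7. Access lost before the guidewire.** Under Section 4, a patient whose radial access is abandoned before guidewire insertion is not enrolled and leaves the procedural-success denominator. Under the description in Section 13.3, the same patient would count if consented, eligible and treated. The two sections must be reconciled.

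**The case against.** The strongest reply is that the point rests on silence. No passage gives sites discretion over whom to enroll, the eligibility criteria are broad and exclude nobody for comorbidity, and the target population is already conditional on radial access being planned. Leaving out patients unsuited to radial access defines that population and does not bias it. The separate monitoring plan is not among the documents and could contain a log. All of this stands. It means that patient selection is a possibility and not a finding, and that only selection after radial access has been scheduled would count.

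A reader might go further in three ways, none of which the documents support:
- **That the enrolled patients will be an enriched, easier group.** This is established for operators only. For patients, no document shows presence or direction.
- **That the true failure rate is some multiple of the reported one.** It is tempting to start from the cited series, where "Twenty-seven cases, representing 1.8%, required crossover to transfemoral access", give that rate to the enrollees and add worse outcomes for those passed over. But that series comprised 1,512 consecutive procedures, so its rate is the nearest the documents have to an unselected figure. The number passed over and their crossover rate would be invented.
- **That the 20-procedure threshold shows operator restriction inflates the primary rates.** Section 1 relates experience in that 60-patient series to fluoroscopy, puncture, procedure and examination times, and does not tie it to crossover, technical success or radial complications. Section 3.1 speaks of patients, and Section 9.1 states the operator restriction openly as a risk measure.

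It can also be said that any bias is lost in the sampling error. In the scenarios above it is no larger than that error. But the planned intervals disclose sampling error and say nothing about selection, so the report would still leave the reader unable to judge it.

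**Conclusion.** The point holds as a gap in design and reporting. The protocol claims real-world rates but neither requires consecutive offers nor provides a record of eligible patients not enrolled, and its existing safeguards cannot reveal selection within a site. The size is unknown: nil if those passed over resemble those enrolled, and from 0.24 points lower (1.36%) to 1.6 points higher (3.2%) in the other scenarios, all within the sampling error at n = 100. These values rest on an assumed 1.6% rate among enrollees and on assumed f and k.

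Separately, the rates apply to operators experienced in radial visceral access, and the conclusions should say so. None of this invalidates the registry. It is an inexpensive improvement worth making before enrollment proceeds. The assessment covers the protocol text alone; a log set out in the monitoring plan would meet part of it.

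**What to change.** - **Section 4.2:** require each site to offer participation to consecutive patients scheduled for on-label HydroPearl embolization via radial access until its cap is reached.
- **Log:** each site keeps a minimal anonymized list with procedure type, offered or not, consented or not, and reason not enrolled, including access abandoned before guidewire insertion.
- **Reporting:** give the enrolled/eligible ratio by site alongside the primary evaluations. Reconcile the meanings of enrolled in Sections 4 and 13.3 so that the ratio and the procedural-success denominator are unambiguous.
- **Conclusions:** state that the rates apply to operators experienced in radial visceral access.

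The cost is one sentence in Section 4.2, a short log, a small table and a line of wording. The downside is some coordinator time and possibly a slightly less favorable success rate. It adds no patients or visits and does not alter how procedures are performed.
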